3.2. Test Articles

Table 1: Test Article Labels

Test Article	Label
ACUVUE OASYS® with Transitions™	Test
ACUVUE OASYS®	Control
All Test Articles	Total

3.3. Targeted Study Population and Sample Size

Approximately 120 subjects will be enrolled to ensure that at least 105 subjects will complete the study. Enrolled subjects will be habitual wearers of spherical contact lenses. All subjects will be the age of 18 and \leq 49 years old. Eligible presbyopes will be those that wear full distance contact lenses in both eyes, then wear reading glasses over them. Subjects will be randomized to either Test/Control/Control or Control/Test/Test. Each lens will be worn for approximately 2 weeks in a bilateral fashion as DW totaling in a study duration of approximately 42 days (6 weeks) per subject.

Table 2: Planned Enrollment Strategy by Lens type and Site

	Test	Control	Total
Enrolled	60	60	120
Randomized	57	57	114
Completed	54	54	108
Number of enrolled per site	10	10	20

3.4. Test Article Allocation and Masking

A computer-generated randomization scheme will be used to randomly assign subjects, in blocks of 2, to one of the two possible lens wear sequences (TEST/CONTROL/CONTROL or CONTROL/TEST/TEST). The random scheme will be generated using the PROC PLAN procedure from SAS Software Version 9.4 or higher (SAS Institute, Cary, NC).

The study site must follow the randomization scheme provided and complete enrollment according to the randomization list and not pre-select or assign subjects. The randomized assignment of subjects will be performed at the first visit prior to the first fitting. The following must have occurred prior to randomization:

- Informed consent has been obtained
- Subject meets all the inclusion / exclusion criteria
- Subject history and baseline information has been collected.

Complete masking is impossible due to the functioning nature of the Test lens. However, both the Test and Control were overlabeled in order to reduce bias as much as possible since the Control lens may be the subject's habitual lens by chance. Therefore, the study is partially-subject masked (Control lens only).

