5.2. Masking

Complete masking is impossible due to the functioning nature of the Test lens. The Control lens will be over-labeled to mask the identity since the Control lens may be the subject's habitual lens by chance. Therefore, the study is partially-subject masked (Control lens only).

Under normal circumstances, the mask should not be broken until all subjects have completed the study and the database is finalized. Otherwise, the mask should be broken only if specific emergency treatment/course of action would be dictated by knowing the treatment status of the subject. In such cases, the investigator may in an emergency contact the medical monitor. In the event the mask is broken, the sponsor must be notified before the mask is broken. The date, time, and reason for the unmasking must be documented in the source document. The investigator is also advised not to reveal the study treatment assignment to the study site or sponsor personnel.

Subjects who have had their treatment assignment unmasked are expected to return for all remaining scheduled evaluations. Subjects who are discontinued may be replaced.

If the test article is randomized, the order will be based on the randomization scheme assigned to the study site. The study site will follow the randomization scheme provided and will complete enrollment according to the randomization list and will not pre-select or assign subjects.

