5.3. Procedures for Maintaining and Breaking the Masking

The test articles mask shall not be broken unless information concerning the lens type is necessary for the urgent medical treatment of a subject. The Sponsor must be notified before the mask is broken.

When dispensing test articles, the following steps should be followed to maintain randomization codes:

1. Investigator or designee (documented on the Delegation Log) will consult the lens fitting schedule/randomization scheme to obtain the test article assignment for that subject prior to dispensing
2. Investigator or designee will record the subject's number on the appropriate line of the randomization scheme
3. Investigator or designee will pull the appropriate test articles from the study supply. All test articles that are opened, whether dispensed (placed/fit on eye or dispensed outside the clinical site) or not, must be recorded on the Test Article Accountability Log in the "Dispensed" section

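### Fixed blocks of 2 from a site-level list, with no concealment described, let sites deduce every second assignment before they settle the next subject's eligibility

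*SAP*

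**What the plan says.** Both documents randomise "in blocks of 2, to one of the two possible lens wear sequences" (SAP 3.4; Protocol 5.1 has the same rule), using a PROC PLAN list. On the level of the list, Protocol 5.2 says that "the order will be based on the randomization scheme assigned to the study site".

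Protocol 5.3 describes how the list is used. The investigator or a designee "will consult the lens fitting schedule/randomization scheme to obtain the test article assignment for that subject prior to dispensing", then has to "record the subject's number on the appropriate line of the randomization scheme" and pull the lenses from stock.

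On masking, Protocol 5.2 says that "Complete masking is impossible due to the functioning nature of the Test lens". Only the subject is masked, and only to the identity of the Control lens. Protocol 5.2 and 6.4 over-label the Control lens alone, while SAP 3.4 says "both the Test and Control were overlabeled in order to reduce bias as much as possible". The two should be reconciled, but neither version masks the investigator.

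On timing, SAP 3.4 says: "The randomized assignment of subjects will be performed at the first visit prior to the first fitting". Consent, eligibility and baseline data must come first. The safeguard offered is an instruction to follow the list and not to pre-select subjects. Sealed envelopes and central or web release are not described. IVRS appears in the SAP's abbreviation list and nowhere else.

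**The concern.** Randomisation protects against selection only if the person who accepts a subject does not know what that subject will receive. With two sequences in blocks of 2, the first assignment in a block determines the second. Site staff know the first because they look it up and dispense it, and the Test lens shows itself in use. The block size is printed in the protocol that sites hold.

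A site can therefore know the next sequence while it is still judging whether the next candidate qualifies. Some of that judgement is discretionary. The subject must appear able and willing to comply (Protocol 3.2), slit lamp findings are graded by eye, and a subject who fails on slit lamp may return for a second Baseline (step 1.10). At stake is whether the two sequence groups are comparable at entry.

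**Working it through.** **Inputs.** Block size 2 and two sequences (Protocol 5.1, SAP 3.4). Site-level scheme (Protocol 5.2). 20 subjects enrolled per site, 10 per column, and 120 in total (SAP Table 2). Six sites (site index in the SAP models).

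**Planned numbers reproduced.** 6 × 20 = 120 and 6 × 10 = 60 per column, as in Table 2. Each site then has 20 / 2 = 10 complete blocks.

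**Assignments known with certainty.** In a balanced block of size b with m = b/2 places per sequence, assignments become certain once one sequence is used up. Full enumeration of the possible blocks gives an expected share of 1/(m + 1).

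- b = 2: 1/2, which is 10 of 20 per site and 60 of 120.
- SAP Table 2 also shows 114 randomised. On that count the figure is at most 57.

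**Assignments guessed correctly**, always guessing the sequence with more places left:

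- b = 2: (0.5 + 1) / 2 = 75.0%.
- b = 4: the four positions give 1/2, 2/3, 2/3 and 1, so (0.5 + 0.667 + 0.667 + 1) / 4 = 70.8%.

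| Block size (known to the site) | Certain | Of 120 | Guessed correctly |
|---|---|---|---|
| 2 | 50.0% | 60 | 75.0% |
| 4 | 33.3% | 40 | 70.8% |
| 6 | 25.0% | 30 | 68.3% |
| 8 | 20.0% | 24 | 66.6% |

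If staff could read the list ahead, every assignment would be known at any block size.

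**Does selection reach the lens contrast?** Suppose selection makes Test/Control/Control subjects differ from Control/Test/Test subjects by a constant s, with no true lens effect. Take the SAP 11.1 visual acuity equations with Carry1 read as set by sequence, and subtract one sequence from the other in each period:

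- Period 1: β1 + β2 = s
- Period 2: −β1 + β2 + β3 = s
- Period 3: −β1 + β2 − β3 = s

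Adding periods 2 and 3 gives β2 − β1 = s. With period 1 this gives β1 = 0, β2 = s and β3 = 0. The shift goes wholly into the sequence term. The CLUE comfort equations have the same structure.

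Two qualifications apply:

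- If Carry1 is coded by the preceding lens and the minus sign printed in period 3 is kept, the period 3 equation becomes identical to period 2. Three effects then rest on two equations and cannot be separated.
- The Protocol 14.5 equations flip the sequence sign in period 2. The same algebra then gives β1 = −s. SAP section 1 says that the SAP supersedes the protocol, so this version should not be the one used.

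**Where assignment falls in Visit 1.** Eligibility is settled at step 1.13, the lens is assigned at 1.15, fit is graded at 1.22, and continuance with investigator approval is 1.23. Only decisions up to step 1.13 can influence which sequence a subject receives.

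**The case against.** The strongest reply is that this is a crossover. Every subject wears both lenses, so the lens comparisons are largely within subject, and under the SAP equations a constant difference between sequences leaves β1 unbiased. That stands, given the carryover coding assumed above.

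A reader might infer more than the documents support:

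- *That the list lies open and all assignments are known.* This is not stated. Protocol 5.3 and 13.4.1 mention randomisation codes, so the list may be coded. A code would not rescue a block of 2, however, because the first subject's lenses still reveal the second subject's sequence.
- *That continuance, investigator approval or early discontinuation can steer allocation.* These come after assignment, when staff know the lens under any release system. Better concealment would not change them.
- *That Control/Test/Test subjects count double in the fit endpoint.* They supply 2 periods × 2 eyes = 4 Test eye-periods against 2 in the other sequence. But SAP 11.1 builds the fit proportion from a linear predictor in which the sequence coefficient is weighted one half, so the raw count does not carry through the planned model. It could matter in a reduced model without sequence, which the SAP allows if the full model does not converge.
- *That the fit rate would move materially.* No eligibility criterion concerns lens fit, fit is first graded after assignment, and the pooled historical data show 0 (protocol) or 1 (SAP) unacceptable fits.
- *That the interim test is biased.* After the first period the two lenses have been worn by different subjects, so a comparison there is between groups. But SAP section 9 limits the interim to description, with no statistical analysis.

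**Conclusion.** The point holds as a modest, avoidable weakness in allocation. Half of the assignments (10 of 20 per site, 60 of 120) can be deduced in advance, and about 75% can be guessed. This assumes that blocks run within site, as Protocol 5.2 indicates, that they are filled, and that staff know the block size and the earlier assignments.

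The route is limited to the eligibility decision before randomisation, including the repeat Baseline. Exposure is mainly to comparability between the sequences and to the descriptive first-period interim, and slightly to the Test-only fit rate. The documents give no basis for putting a number on any bias, and nothing here shows that the non-inferiority conclusions for the lens contrasts are at risk.

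**What to change.** In Protocol 5.1 and SAP 3.4:

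1. State a concealment method. Release each assignment singly, only after eligibility has been recorded at step 1.13, by sequentially numbered sealed slips. The EDC system could do this instead if it supports it; Protocol 15.1 describes it for data capture only. Amend the list-consultation steps in Protocol 5.3 to match.
2. Replace fixed blocks of 2 with randomly varying blocks within site, for example 4 and 6, and keep the sizes out of documents that sites hold.

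The first change is the essential one, because known blocks of 4 or 6 alone leave 33% or 25% of assignments certain and about 71% or 68% guessable.

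The cost is a new PROC PLAN list, a small change in release procedure (more if the EDC has to be configured for it), and a slightly larger possible imbalance between sequences within a site.

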3.5. Time and Event Schedule

Table 3: Time and Events Schedule

Procedure	Baseline	Trial Fit & Dispense	Follow-up	Unscheduled	Exit
Visit	1	1, 2, 3	2, 3, 4	PRN	4
Visit Window	-	-	13-15 Days	-	-
Estimated Visit Duration	-	V1: 2 hours	V2, 3: 1 hour V4: 1.5 hours	-	-
Informed consent	✓	-	-	-	-
Eligibility screening	✓	-	-	-	-
CLUE Baseline Questionnaire	✓	-	-	-	-
GSI Background Questionnaire	✓				
Other Questionnaires	✓	-	✓	-	-
Subject demographics	✓	-	-	-	-
General health and medication history	✓	-	-	-	-
Subject's own contact lens information	✓	-	-	-	-
Habitual lens care	✓	-	-	-	-
Entrance visual acuity	✓	-	-	-	-
Spherocylindrical refraction and BVA	✓	-	-	✓	✓
Slit lamp biomicroscopy	✓	-	✓	✓	-
Expanded Conjunctival Redness	✓	-	✓	✓	-
Expanded Corneal Staining	✓	-	✓	✓	-
Trial fitting lens information	-	✓	-	-	-
Lens Damage	-	✓	-	-	-
Distance spherical over-refraction	-	✓	✓	-	-
Lens modification	-	✓	-	-	-
Visual acuity	-	✓	✓	✓	-
logMAR acuity	-	-	✓	-	-
Contrast sensitivity (site 1036)	-	-	✓	-	-
Lens fitting assessment	-	✓	✓	*	-
Lens dispensing information and criteria	-	✓	-	-	-
Patient instructions	-	✓	-	-	-
Lens information	-	-	✓	✓	-

Procedure	Baseline	Trial Fit & Dispense	Follow-up	Unscheduled	Exit
Visit	1	1, 2, 3	2, 3, 4	PRN	4
Visit Window	-	-	13-15 Days	-	-
Estimated Visit Duration	-	V1: 2 hours	V2, 3: 1 hour V4: 1.5 hours	-	-
Compliance	-	-	✓	✓	-
Wearing times	-	-	✓	✓	-
CLUE Follow-Up Questionnaire	-	-	✓	*	-
GSI Product Performance Questionnaire	-	-	✓	*	-
Symptoms	-	✓	✓	✓	-
Lens preference	-	-	V3	-	-
Surface characteristics	-	-	✓	*	-
Chief complaint, diagnosis, treatment	-	-	-	✓	-

* if wearing study contact lenses

4. STUDY ENDPOINTS

4.1. Primary Endpoints

Primary Efficacy Endpoints:

CLUE Overall Comfort

Overall comfort scores will be assessed using the Contact Lens User Experience (CLUE™)¹ questionnaire at the two-week follow-up. CLUE is a validated patient-reported outcomes questionnaire to assess patient-experience attributes of soft contact lenses (comfort, vision, handling, and packaging) in a contact-lens wearing population in the US, ages 18-65. Derived CLUE scores, using Item Response Theory (IRT), follow a normal distribution with a population average score of 60 (SD 20), where higher scores indicate a more favorable/positive response. A 5 point increase in an average CLUE score translates into 10% shift in the distribution of scores for a population of soft contact lens wearers¹. The handling scores will be generated using the flexMIRT software version 3 or higher (Chapel Hill, NC).

Distance Monocular Contact Lens Visual Acuity

Distance monocular contact lens visual performance (logMAR) is assessed for each subject eye at the two-week follow-up evaluation using EDTRS charts under two lighting conditions, (1) Bright illumination low contrast and (2) Dim Illumination High Contrast.

Vision Satisfaction in Bright Lighting

Vision satisfaction in bright lighting will be assessed using the individual item [REDACTED] “I was satisfied with the quality of my vision in bright lighting” from the CLUE™ questionnaire.

This item uses the response scale, 1: Strongly Disagree, 2: Disagree, 3: Neither Agree nor Disagree, 4: Agree and 5: Strongly Agree.

Primary Safety Endpoints:

Slit Lamp Findings (Grade 3 or Higher)

Slit Lamp Findings will be assessed using the FDA Grading scale ranging from 0 to 4, where Grade 0 represents the absence of findings and 1 to 4 representing successively worse findings (i.e. Grade 1=trace, Grade 2= mild, Grade 3=moderate and Grade 4= severe). The assessment will include conjunctival injection, corneal edema, corneal neovascularization, corneal staining, tarsal abnormalities or any other complication. SLF assessments will be conducted for each subject eye at all scheduled study visits(Fitting [Visit 1] and 2-Week Follow-up [Visit 2]). The percentage of eyes with Grade 3 or higher slit lamp findings will be analyzed; eyes with multiple events will be counted only once.

Fit Acceptance Rate

Acceptable lens fit will be assessed for each subject eye at all scheduled study visits (fitting [visit 1] and follow-up [visit 2]). Fit acceptance rate will be based on the lens fit acceptance of eyes wearing the Test lens only. Fit rates of the Control lens will also be collected but are not a primary endpoint.

